## **(1)Research background**

Septic shock represents the severe phase of infection-induced systemic inflammatory response syndrome (SIRS), characterized by a complex pathophysiological mechanism. It is primarily manifested as vasodilation, capillary leakage, and myocardial depression triggered by SIRS, with persistent hypotension, tissue hypoperfusion, and multiple organ dysfunction resulting from insufficient effective circulating blood volume as the main clinical features. With a mortality rate exceeding 40%, it ranks among the common critical illnesses in the emergency department. International guidelines for the management of septic shock highlight that early goal-directed fluid resuscitation is the cornerstone of septic shock treatment. It aims to alleviate the systemic damage caused by shock by rapidly restoring effective circulating blood volume and increasing tissue oxygen delivery, thereby improving prognosis and enhancing quality of life. Consequently, fluid resuscitation holds an irreplaceable role in the management of septic shock, and the first 6 hours after shock recognition, in particular, is designated as the "golden resuscitation period" . However, both excessive and insufficient fluid resuscitation may exacerbate the condition and elevate the risk of complications such as pulmonary edema, acute respiratory distress syndrome (ARDS), and acute kidney injury (AKI). Thus, how to rapidly and accurately assess a patients volume status and cardiac function in the emergency department, formulate individualized fluid resuscitation strategies, achieve precise volume management, and avoid over-resuscitation or under-resuscitation has become an urgent clinical challenge.

Traditional fluid resuscitation strategies rely predominantly on static parameters such as central venous pressure (CVP), mean arterial pressure (MAP), and urine output for guidance. However, these indices have inherent limitations in assessing volume responsiveness and predicting fluid resuscitation efficacy, failing to accurately and dynamically reflect a patients volume status or cardiac preload responsiveness. In recent years, with advances in hemodynamic monitoring technologies, dynamic evaluation of volume responsiveness has emerged as a key strategy for optimizing fluid resuscitation and improving patient outcomes.

Critical care ultrasound, for instance, enables rapid bedside assessment of cardiopulmonary function by real-time visualization of indices including inferior vena cava variability, ventricular wall motion, volume responsiveness, and lung water content, thereby providing visual evidence to guide early fluid resuscitation. Non-invasive cardiac output monitoring, conversely, dynamically tracks circulatory function through quantification of parameters such as cardiac output and stroke volume variability, offering objective data to evaluate resuscitation efficacy. Accordingly, critical care ultrasound and non-invasive cardiac output monitoring have increasingly become valuable clinical adjuncts in guiding fluid resuscitation for patients with septic shock in the emergency department.

## **(2) research objective**

1. Main Objective: This study explores the value of critical care ultrasound and non-invasive cardiac output monitoring in fluid resuscitation for emergency department patients with septic shock, providing evidence for optimizing hemodynamic management of septic shock, improving patient prognosis, and guiding clinical selection of appropriate monitoring modalities.

2. Secondary purpose: This study aims to explore the value of critical care ultrasound and non-invasive cardiac output monitoring in fluid resuscitation for emergency department patients with septic shock, to inform optimized hemodynamic management, improve prognosis, and guide clinical selection of monitoring modalities.

## **(3) Research Design Types, Principles, and Test Procedures**

### **1. Research Design**

Subjects were recruited from patients with septic shock admitted to the Emergency Department of Guangzhou Panyu District Central Hospital between July 2023 to July 2025. Demographic data of patients, including gender, age, and underlying diseases, were collected, along with mean arterial pressure, baseline lactate levels, and vital signs at enrollment. Records were made of the total fluid volume administered within the first 6 hours after patients were randomized into groups, the achievement of resuscitation targets,

blood lactate levels, blood pressure, and the incidence of complications such as pulmonary edema and renal injury. Additionally, the use of vasoactive agents (e.g., dopamine, epinephrine/norepinephrine), mechanical ventilation support, and antibiotics was documented. Patients were followed up to record the duration of emergency department stay, total hospital stay, 28-day mortality, and adverse events occurring during the study period (e.g., severe arrhythmias, anaphylactic shock).

After patients met the inclusion criteria and signed the informed consent form, random numbers were generated using SPSS 26.0 statistical software to randomly assign 73 participants to the critical care ultrasound group and the non-invasive cardiac output group. The generated random allocation table was prepared in duplicate, which were sealed and stored by the statistician and research coordinator respectively to prevent premature disclosure of group allocation information.

In the critical care ultrasound group, patients underwent immediate bedside assessment using a Philips EPIQ 5 color Doppler ultrasound system equipped with both phased-array (1.5-4.0 MHz) and convex-array (2.0-5.0 MHz) transducers. The initial ultrasound evaluation was completed within 10 minutes of enrollment and included comprehensive hemodynamic monitoring: inferior vena cava diameter (IVC) and collapsibility index (IVC-CI) for volume status assessment, left ventricular ejection fraction (LVEF) and end-diastolic volume (LVEDV) for cardiac function evaluation, ventricular wall motion analysis, along with pulmonary B-line quantification to assess pulmonary edema. This protocol ensured real-time, comprehensive evaluation of both cardiac function and fluid status to guide resuscitation. Ultrasound reassessment was performed every 1-2 hours to dynamically adjust both the volume and rate of fluid administration until predefined resuscitation targets were achieved.

In the noninvasive cardiac output monitoring group, continuous hemodynamic assessment was performed using the NICOM system based on thoracic bioreactance technology. Following the manufacturers standard operating procedures, four electrode pads were placed at bilateral subclavicular areas and the left subcostal region. Monitoring commenced immediately after

enrollment, with baseline parameters recorded after signal stabilization ( $\leq 5$  minutes), including cardiac output (CO), stroke volume (SV), stroke volume variation (SVV), and systemic vascular resistance (SVR). The system automatically updated these parameters every 30 seconds and displayed them in real-time on the monitor screen. Fluid resuscitation was dynamically adjusted according to these continuous measurements until achieving the predefined therapeutic targets.

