# **Clinical research protocol**

Project name: The value of critical care ultrasound and noninvasive cardiac output monitoring in guiding fluid resuscitation for septic shock in the emergency department

leading unit:Guangzhou Panyu Central Hospital, Guangzhou, Guangdong, China

project leader:[name]

Department: Emergency Department

Research period: July 2025 to July 2025

Version No.: V 1.0

Version Date: May 22, 2023

|                                      |   |
|--------------------------------------|---|
| object name                          | The value of critical care ultrasound and non-invasive cardiac output monitoring in fluid resuscitation for emergency department patients with septic shock.  |
| goal of study                        | This study explores the value of critical care ultrasound and non-invasive cardiac output monitoring in fluid resuscitation for emergency department patients with septic shock, providing evidence for optimizing hemodynamic management of septic shock, improving patient prognosis, and guiding clinical selection of appropriate monitoring modalities.  |
| research design               | Subjects were recruited from patients with septic shock admitted to the Emergency Department of Guangzhou Panyu District Central Hospital between July 2023 to July 2025. Demographic data of patients, including gender, age, and underlying diseases, were collected, along with mean arterial pressure, baseline lactate levels, and vital signs at enrollment. Records were made of the total fluid volume administered within the first 6 hours after patients were randomized into groups, the achievement of resuscitation targets, blood lactate levels, blood pressure, and the incidence of complications such as pulmonary edema and renal injury. Additionally, the use of vasoactive agents (e.g., dopamine, epinephrine/norepinephrine), mechanical ventilation support, and antibiotics was documented. Patients were followed up to record the duration of emergency department stay, total hospital stay, 28-day mortality, and adverse events occurring during the study period (e.g., severe arrhythmias, anaphylactic shock). |
| Total number of cases studied | 60 cases (30 cases in each group)   |

|                            |   |
|----------------------------|---|

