| statistical method | 
This study adopted a prospective randomized controlled design, and the sample size was estimated using PASS 15.0 software. Based on the difference in 6-hour fluid resuscitation volume between the two groups in the pilot study (mean difference 1261 mL, standard deviation 3155 mL), <math>\alpha=0.05</math> (bilateral) was set <math>\beta=0.2</math>. Calculated to require 27 cases per group, considering a 20% dropout rate, 60 cases were ultimately included. Use SPSS 26.0 to generate block random sequences (block size 4), and allocate concepts through sealed envelopes. The normality of the measurement data was confirmed by Shapiro Wilk test, and those that conform to the normal distribution were expressed as mean <math>\pm</math> standard deviation. Independent sample t-test was used for inter group comparison; non normally distributed individuals are represented by the median (interquartile range) and Mann Whitney U test is used. The categorical data is presented in terms of the number of cases (%), and the comparison between groups is conducted using the chi square test or Fishers exact test (when the theoretical frequency is less than 5). The main outcome (28 day mortality rate) was plotted using Kaplan Meier survival curve, and inter group differences were analyzed using log rank test, and HR (95% CI) was calculated. Secondary outcomes (such as fluid dosage, MAP, etc.) report mean difference (MD) or relative risk (RR) and their 95% confidence intervals. All tests are bilateral, and <math>P<0.05</math> is considered statistically significant. Perform Bonferroni correction on secondary outcomes (<math>\alpha=0.05/6 \approx 0.008</math>). Multivariate Cox regression was used to adjust for confounding factors such as age and baseline lactate, and sensitivity analysis included protocol set (PP) and intention to treat (ITT) analyses. The statistical software used is R 4.3.1 (R Foundation) and SPSS 26.0 (IBM).
 |

|                        |                        |
|------------------------|------------------------|
| Research period | July 2023 to July 2025 |
|------------------------|------------------------|

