##### 3. Elimination criteria

Subjects who have been enrolled in the study but meet one of the following criteria should be excluded:

(1) After inclusion, those who did not meet the inclusion criteria or met the exclusion criteria were found.

(2) Those who have not used test drugs / interventions.

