## **(10)Statistical processing**

This study adopted a prospective randomized controlled design, and the sample size was estimated using PASS 15.0 software. Based on the difference in 6-hour fluid resuscitation volume between the two groups in the pilot study (mean difference 1261 mL, standard deviation 3155 mL),  $\alpha=0.05$  (bilateral) was set  $\beta=0.2$ , Calculated to require 27 cases per group, considering a 20% dropout rate, 60 cases were ultimately included. Use SPSS 26.0 to generate block random sequences (block size 4), and allocate concepts through sealed envelopes. The normality of the measurement data was confirmed by Shapiro Wilk test, and those that conform to the normal distribution were expressed as mean  $\pm$  standard deviation. Independent sample t-test was used for inter group comparison; non normally distributed individuals are represented by the median (interquartile range) and Mann Whitney U test is used. The categorical data is presented in terms of the number of cases (%), and the comparison between groups is conducted using the chi square test or Fishers exact test (when the theoretical frequency is less than 5). The main outcome (28 day mortality rate) was plotted using Kaplan Meier survival curve, and inter group differences were analyzed using log rank test, and HR (95% CI) was calculated. Secondary outcomes (such as fluid dosage, MAP, etc.) report mean difference (MD) or relative risk (RR) and their 95% confidence intervals. All tests are bilateral, and  $P<0.05$  is considered statistically significant. Perform Bonferroni correction on secondary outcomes ( $\alpha=0.05/6 \approx 0.008$ ). Multivariate Cox regression was used to adjust for confounding factors such as age and baseline lactate, and sensitivity analysis included protocol set (PP) and intention to treat (ITT) analyses. The statistical software used is R 4.3.1 (R Foundation) and SPSS 26.0 (IBM).

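### The protocol randomises 73 participants in section (3) but gives 60 cases in the synopsis and section (10), and 60 does not hold the stated 20% dropout allowance on 27 per group

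*Protocol*

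**What the plan says.** Section (3), under Research Design, describes generating random numbers after eligibility and consent, "to randomly assign 73 participants to the critical care ultrasound group and the non-invasive cardiac output group". It gives no split by arm.

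The synopsis row for the total number of cases reads "60 cases (30 cases in each group". Its statistical row says: "Calculated to require 27 cases per group, considering a 20% dropout rate, 60 cases were ultimately included". Section (10) repeats that derivation, ending "considering a 20% dropout rate, 60 cases were ultimately included". The inputs given there are a pilot difference in 6-hour fluid volume ("mean difference 1261 mL, standard deviation 3155 mL"), two-sided alpha 0.05 and beta 0.2. Allocation is in blocks of 4.

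Two other statements bear on which number is which. Section (4), under Elimination criteria, says: "Subjects who have been enrolled in the study but meet one of the following criteria should be excluded"; the criteria are ineligibility discovered after inclusion and not having received the intervention. Section (10) names the analysis sets only in this clause: "sensitivity analysis included protocol set (PP) and intention to treat (ITT) analyses".

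**The concern.** The protocol gives two totals and does not say how they relate. They could be different quantities, for example 73 randomised and 60 left after the removals in section (4). The text does not say so, and section (10) presents 60 as the size with dropout already added. On that account 60 is an enrolment figure, not what remains after losses.

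The intention-to-treat set is therefore 73 patients on one reading and 60 on the other. If 73 were randomised and 60 analysed, 13 randomised patients are unaccounted for, in a trial whose main outcome in sections (7) and (10) is 28-day mortality with about 30 patients per arm. If 60 were randomised, the protection against 20% dropout that the protocol claims does not exist.

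**Working it through.** **Inputs.** 73 randomised (section (3)); 60 in total, 30 per group (synopsis); 27 per group required, 20% dropout, 60 included (synopsis and section (10)); difference 1261 mL, standard deviation 3155 mL, two-sided alpha 0.05, power 0.80, blocks of 4 (section (10)).

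**Step 1: reproduce 60 from 27 per group and 20% dropout.**
- Dividing by the retained fraction: 27/(1 − 0.20) = 33.75, so 34 per group and 68 in total.
- Multiplying by 1.2, a looser convention: 27 × 1.2 = 32.4, so 33 per group and 66 in total; on the total, 54 × 1.2 = 64.8, so 65.
- Neither convention gives 60. Sixty is 68 − 60 = 8 short of the first.

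**Step 2: what 60 does cover.**
- 54/60 = 0.90, a 10% loss.
- At 20% loss, 60 × 0.8 = 48, or 24 per group, against the stated 27 per group (54 in total).

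**Step 3: does 73 fit anywhere?**
- 73 − 60 = 13, and 13/73 = 0.178.
- As an inflation of 54, 73 covers 1 − 54/73 = 0.26, a 26% loss, which the protocol does not mention.
- As an inflation of 60 for 20% loss, the results would be 60 × 1.2 = 72 or 60/0.8 = 75. Seventy-three lies between them, but this would make 60 the evaluable number, contrary to section (10).
- 60 = 15 × 4 fills complete blocks. 73 = 18 × 4 + 1 does not, and being odd it cannot be two equal arms. An incomplete last block is possible, so this is not an error in itself. It does mean that 30 per group cannot describe everyone randomised if 73 were.

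**Step 4: does 27 per group follow from the stated inputs?**
- Standardised difference: 1261/3155 = 0.400.
- Normal approximation: n = 2 × (1.960 + 0.842)² × (3155/1261)² = 98.3, so 99 per group. A two-sided t-test calculation gives 99.2, so 100 per group.
- t-test power on these inputs is 0.302 at 27 per group and 0.273 at 24 per group.

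The 68 in Step 1 is therefore conditional on the protocol's 27 and is not an adequate size for the stated inputs.

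**The case against.** Three statements agree on 60, one adds 30 per group, and 60 fits blocks of 4 while 73 does not. This suggests that 60 is the plan and 73 a stray or later count. The inference is reasonable but remains an inference: the synopsis and section (10) describe the 60 as cases studied or included, which leaves open that more were randomised.

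The dropout shortfall has little inferential weight, because power on the stated inputs is about 30% at 27 per group and 27% at 24. That is right, and no fall from 80% power is claimed here. The error is in a stated safeguard, and it stands whatever 73 means, because it uses only the figures in one sentence.

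It can also be said that restating the allowance as 10% fits the assumption to the total, since 20% is the only expected loss the protocol gives. This holds to the extent that 10% must be worded as what 60 can absorb, not as a forecast.

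Finally, intention to treat is named only among the sensitivity analyses, and analysing all 73 has to be squared with the removals in section (4). Both qualifications stand. Neither removes the need to know how many were randomised.

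**Conclusion.** The concern holds on both counts. The protocol gives 73 and 60 without connecting them, a gap of 13 patients or 17.8% of 73. Separately, 60 is not 27 per group with 20% dropout, which gives 65 to 68 depending on the convention; it allows for 10%. The first count rests on the current text of the synopsis and sections (3) and (10). The second takes the protocol's 27 per group as given, although that figure does not itself follow from 1261 mL and 3155 mL. Which total is true cannot be settled from the document; only the sponsor can say. The number to be randomised is a protocol figure, so a separate analysis plan would not cure the conflict.

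**What to change.** State one number to be randomised and, separately, the number evaluable, and use both consistently in the synopsis and sections (3) and (10).

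- **If 60 were randomised:** correct the 73 in section (3), and replace the 20% allowance by what 60 supports: 10% loss, 54 evaluable of 60. The cost is text changes and a less favourable stated allowance.
- **If 73 were randomised and 60 are the cases studied:** say so, give the split by arm, account for the other 13 by arm and reason, and analyse all 73 by assigned arm. For that analysis, reconcile the post-enrolment removals in section (4) with intention to treat: the elimination criteria, the exclusion for withdrawal or transfer within 24 hours of admission, and the suspension and drop-out criteria. The cost is retrieving any data not already held on the 13, and an analysis of all 73, besides the text changes.

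Neither branch needs extra patients. In both, do not present 27 per group or 68 in total as adequate, since the stated inputs need about 100 per group before dropout.

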| case selection      | 
Inclusion criteria:
 
(1) diagnosis of septic shock in accordance with the Surviving Sepsis Campaign International; (2) receipt of initial fluid resuscitation in the emergency department with a hospital stay of at least 6 hours; (3) age <math>\geq</math> 18 years; (4) provision of informed consent.
 
excluded criteria:
 
(1) contraindications to rapid fluid administration (e.g., end-stage renal disease, end-stage heart failure, acute pulmonary edema); (2) inability to comply with treatment, such as patients with severe trauma, burns, cancer undergoing chemotherapy, pregnant or lactating women, and those with mental illness; (3) withdrawal from treatment or transfer to another facility within 24 hours of admission.
 |
| Treatment plan      | 
Both groups were managed according to the 2021 Surviving Sepsis Campaign (SSC) International Guidelines for septic shock resuscitation, including: (1) early antimicrobial therapy, (2) vasopressor support (with norepinephrine as first-line), and (3) organ function support. The key difference between groups lay in the fluid resuscitation monitoring approach (critical care ultrasound vs. noninvasive cardiac output monitoring)
   |
| efficacy evaluation | 
The main efficacy indicators: emergency department length of stay, total hospital stay.
 
Secondary efficacy indicators: regarding total fluid volume within the first 6 hours of resuscitation, early resuscitation efficacy (time to achieve mean arterial pressure <math>\geq</math>65 mmHg, lactate reduction <math>\geq</math>20% from baseline, or lactate clearance <math>\geq</math> 10%), complication rates (including pulmonary edema, renal injury, and acute respiratory distress syndrome).
   |

|                           |  |
|---------------------------|--|
|                           | Safety evaluation index: 28-day mortality.   |

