### **(6) Observation items and detection time points**

1. Demographic data of patients, including gender, age, and underlying diseases, were collected, along with mean arterial pressure, baseline lactate levels, and vital signs at enrollment.
2. Records were made of the total fluid volume administered within the first 6 hours after patients were randomized into groups, the achievement of resuscitation targets, blood

lactate levels, blood pressure, and the incidence of complications such as pulmonary edema and renal injury.

3. Document the use of vasoactive agents (e.g., dopamine, epinephrine/norepinephrine), mechanical ventilation support, and antibiotics.
4. Record the duration of Emergency Department stay, total hospital stay, 28-day mortality, and adverse events occurring during the study period (e.g., severe arrhythmias, anaphylactic shock).

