## **(7) standards for efficacy appraisal**

The primary outcome was 28-day mortality

Secondary outcomes included the efficacy of initial resuscitation, duration of hospital stay, incidence of complications, and other relevant parameters.

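### Pulmonary edema is compared between arms, but only the ultrasound arm has a protocol test for it, and nothing keeps that test out of the outcome

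*Protocol*

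**What the plan says.** **The outcome.** The synopsis (efficacy evaluation) lists among the secondary indicators "complication rates (including pulmonary edema, renal injury, and acute respiratory distress syndrome". Section (6) has the site record "the incidence of complications such as pulmonary edema and renal injury". Section (7) states: "Secondary outcomes included the efficacy of initial resuscitation, duration of hospital stay, incidence of complications, and other relevant parameters". Section (10) compares categorical data by chi-square or Fisher's exact test, reports mean differences or relative risks for secondary outcomes, and tests these at 0.05/6, about 0.008.

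**The ultrasound arm.** Section (3), Research Design, requires an initial scan within 10 minutes of enrollment, with IVC and left ventricular measures and wall motion, "along with pulmonary B-line quantification to assess pulmonary edema". It continues: "Ultrasound reassessment was performed every 1-2 hours to dynamically adjust both the volume and rate of fluid administration", until targets are met. The components of the repeat scan are not listed.

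**The NICOM arm.** The same section lists the recorded parameters, "including cardiac output (CO), stroke volume (SV), stroke volume variation (SVV), and systemic vascular resistance (SVR", and mentions no lung assessment.

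**The intended contrast.** The synopsis (treatment plan) says: "The key difference between groups lay in the fluid resuscitation monitoring approach".

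The protocol gives no criteria, common test, assessor or masking for the pulmonary edema complication. X-ray and blood gas appear only in section (8), as examinations to set against the non-invasive findings when deciding whether to terminate the experiment.

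**The concern.** The stated purpose of B-line quantification is to assess the same condition that is later compared as a complication, and only one arm receives it. An investigator recording pulmonary edema in the ultrasound arm has information that the NICOM investigator lacks, and no instruction to set it aside. The relative risk could then mix the effect of the monitoring strategy with the effect of looking harder.

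The error could go either way. With equal true rates, the ultrasound arm could appear to cause more edema. With a true benefit of ultrasound guidance, extra detection in that arm could cancel it. The second case matters because section (1) names pulmonary edema among the harms of poorly judged fluid resuscitation that motivate the trial.

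This is more than detail left to an analysis plan. The asymmetry lies in bedside data collection, and an analysis plan cannot supply a lung assessment that one arm never had.

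**Working it through.** The protocol states no figure on this point, so there is none to reproduce. The check has two parts.

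**1. The text, side by side**

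| | Ultrasound arm | NICOM arm |
|---|---|---|
| Lung test in the strategy | B-lines at the initial scan | None listed |
| Later monitoring | Ultrasound every 1-2 hours, components not listed | Flow and resistance values, updated every 30 seconds |
| Edema complication compared | Yes | Yes |
| Outcome criteria | None stated | None stated |

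The asymmetry exists with a single scan. It would be larger if the repeat scans include B-lines.

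**2. Illustration of size**

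Inputs from the protocol: 30 per arm (synopsis; section (3) mentions 73 participants in all, but arm size does not affect the expected rates or their ratio), two-sided testing, and 0.05/6 for secondary outcomes. Assumed, because the protocol gives neither: the true edema rate and the detection probability (sensitivity) in each arm. Specificity is taken as perfect.

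Formula: observed rate = true rate × sensitivity. If true rates are equal, they cancel and the observed RR = sensitivity (ultrasound) / sensitivity (NICOM).

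*Creating a difference* (true rate 20% in both arms):

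- 90% vs 60%: 18% vs 12%, RR = 0.90/0.60 = 1.50. In patients, 30 × 0.18 = 5.4 vs 30 × 0.12 = 3.6.
- 90% vs 70%: 18% vs 14%, RR = 0.90/0.70 = 1.29.
- 95% vs 50%: 19% vs 10%, RR = 0.95/0.50 = 1.90.

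*Hiding a difference* (true rates 20% ultrasound, 40% NICOM):

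- Detection 90% vs 45%: 0.20 × 0.90 = 18% and 0.40 × 0.45 = 18%, RR 1.0.
- Detection 90% in both arms: 18% vs 36%, RR 0.5.

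*False rejection* (exact enumeration of a two-sided Fisher test, 30 per arm, equal true rates of 20%):

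| Detection | Observed | RR | At 0.05 | At 0.05/6 |
|---|---|---|---|---|
| 90% vs 90% | 18% vs 18% | 1.00 | 2.1% | 0.3% |
| 90% vs 70% | 18% vs 14% | 1.29 | 2.9% | 0.4% |
| 90% vs 50% | 18% vs 10% | 1.80 | 6.3% | 1.2% |
| 90% vs 30% | 18% vs 6% | 3.00 | 14.3% | 3.6% |

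The most extreme case run, a true rate of 40% with 90% vs 30%, gives 48.7% and 22.9%. Fisher is used there for comparability, although the expected count of (10.8 + 3.6)/2 = 7.2 would lead the plan to chi-square.

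*Dependence on specificity.* With false positives, observed rate = p × Se + (1 − p)(1 − Sp), where p is the true rate, Se sensitivity and Sp specificity. Take 5% false positives in the ultrasound arm only and detection of 90% vs 50%:

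- p = 20%: 0.18 + 0.80 × 0.05 = 22% vs 10%, RR 2.2.
- p = 40%: 0.36 + 0.60 × 0.05 = 39% vs 20%, RR 1.95.

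The RR is therefore free of the true rate only when specificity is perfect and true rates are equal.

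**The case against.** The strongest reply is that the protocol never links B-lines to the complication outcome. It describes the scan as a guide to resuscitation, and the complication sections do not mention B-lines. That stands. A reader might infer that edema found by B-lines is counted as an event. The text does not say so; it permits such counting because nothing excludes it.

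A reader might also infer that B-lines are quantified at every reassessment. The protocol says "Ultrasound reassessment was performed every 1-2 hours" but lists B-lines only under the initial evaluation. Repetition is plausible, not stated. If B-lines were taken only at entry, they would mostly show edema already present, which section (4) makes an exclusion criterion, and enrolled patients later found to meet an exclusion criterion are to be removed. That weakens the case for incident edema, but it leaves a one-arm test that could lead to a patient being counted, or removed, in that arm only.

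A further tempting inference is that ARDS ascertainment is distorted as well. Nothing in the protocol ties B-lines to the diagnosis of ARDS, so this is not claimed.

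The practical weight is also fairly questioned. In the 90% vs 60% case the arms differ by 5.4 − 3.6 = 1.8 patients, in one component of one secondary outcome. Under the corrected threshold, false rejection at a 20% true rate stays low except with very unequal detection. This stands, but the stricter threshold limits only chance findings. It does not remove bias from the reported relative risk or its confidence interval.

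**Conclusion.** The concern holds as a risk that the protocol leaves open, not as a demonstrated bias. Pulmonary edema is compared between arms, only the ultrasound arm has a test with the stated purpose of assessing it, and no common criteria or exclusion of B-line findings is given.

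The size is illustrative only: a spurious RR of 1.5 (1.29 to 1.9) with equal true rates, or complete masking of a halving from 40% to 20%. These figures rest on assumed detection probabilities, assumed true rates and perfect specificity; the spurious RRs also need equal true rates. None of these can be taken from the protocol. It would go too far to say that the ultrasound arm will show more edema, or that the direction of the bias is known.

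The point is a cheap improvement. It concerns a secondary harm outcome and leaves the trial's other main comparisons untouched.

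**What to change.** In sections (6) and (7), define the pulmonary edema complication by one set of criteria, using data obtained the same way in both arms: clinical signs, oxygenation, and chest X-ray taken in care. Fix one window after randomisation. State that study B-line findings do not count toward the outcome, and report B-lines descriptively in the ultrasound arm only. Where existing staff allow, have events classified from records with arm and B-line results masked.

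The cost is a few sentences of outcome wording, plus some staff time if masked classification is used. No treatment or monitoring changes. There are two downsides. Mild edema seen only on ultrasound is not counted. Some bias remains, because treating clinicians know the B-line results when they order X-rays, so the change reduces unequal detection without removing it.
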